4.2 Number of Patients

A total of 10 patients will be enrolled in this pilot clinical trial. We currently have more than 40 patients that qualify for the study based on the inclusion criteria described below. A patient will be considered enrolled after the first day of ixazomib treatment.

4.3 Duration of Study

Participants will be followed for the entire length of treatment, plus one month. All subjects, including those that receive a kidney transplant and those that do not, will continue to be monitored for one month following the last dose of study drug to monitor for and address potential adverse events from treatment (Final visit on day 373 + 6, - 3). Thereafter, dialysis nephrologists will routinely follow the patients. For those transplanted, data on acute rejection, graft and patient survival will be collected for 6 months after surgery.

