Sensitization in kidney transplant candidates. Alloantibodies (anti-HLA antibodies) arise through previous transplants, blood transfusions, and pregnancy. Currently, 39% of patients on the active kidney transplant waitlist are sensitized, evidenced by a Panel Reactive Antibody (PRA) $\geq 1\%$ (33). Of these, nearly 15,000 are highly sensitized, which means that they have a PRA $\geq 80\%$ (33). Transplant rates vary by PRA, ranging from 143.0 per 100 active waitlist years for candidates with a PRA of less than 1% to only 6.9 for those with a PRA of 98% or higher (33). Median waiting time for kidney transplantation in highly sensitized patients approaches 12 years, which is more than 3 times than for non-sensitized patients (33). As a result, a significant number of highly sensitized patients die before receiving a transplant, outlining the critical importance of desensitization strategies.

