3.2 Secondary Endpoints (efficacy endpoint)

Secondary efficacy endpoint: Successful transplantation in 12 months

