Duration of Treatment and Follow-up. All participants, those that receive a kidney transplant during the defined period and those that do not will be followed for the entire length of treatment, plus one month following the last dose of the study drug. All subjects will be asked to return for a final study visit approximately one month following the last dose of study drug. During this final study visit, subjects will undergo physical examination, bone marrow aspirate collection, CBC, LFT check, ECG and echocardiogram.

Bone Marrow Aspirate Collection Procedure: Subjects will be given the option of having the bone marrow aspirate performed under conscious sedation or local anesthetic only. The bone marrow aspirate will be collected in a transplant clinic room. If the bone marrow aspiration is done under conscious sedation, subjects will be given instructions to fast for six hours before the procedure (medications are allowed) and not to drive themselves home or operate dangerous equipment after the procedure.

Measurement of effect. We will determine the effect of ixazomib by measuring cPRA, whether patients receive a kidney transplant while participating in the study, antibody strength by MFI, and the toxicity (measured by the incidence of adverse events) of the treatment quarterly up to the end of the study.

Ixazomib Administration

All protocol-specific criteria for administration of study drug must be met and documented before drug administration. Study drug will be dispensed only to eligible patients by a member of the study team. Patients should be monitored for toxicity, as necessary, and doses of ixazomib should be modified as needed to accommodate patient tolerance to treatment; this may include symptomatic treatment, dose interruptions, and adjustments of ixazomib dose (see Section 6.3).

Capsules of ixazomib will also be referred to as study drug. Study drug will be supplied by Millennium as capsules 0.5, 2.3, and 3.0 mg ixazomib. The prescribed administration of ixazomib doses in this study is 9 mg ixazomib in a 28 day cycle. Patients should be instructed to swallow ixazomib capsules whole, with water, and not to break, chew, or open the capsules. Ixazomib should be taken on an empty stomach (no food or drink) at least 1 hour before or at least 2 hours after food. Each capsule should be swallowed separately with a sip of water. A total of approximately 8 ounces (240 mL) of water should be taken with the capsules.

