6.12 Termination of Treatment and/or Study Participation

Patients will be informed that they have the right to withdraw from the study at any time for any reason, without prejudice to their medical care. The investigator also has the right to withdraw patients from the study for any of the following reasons:

- If study drug is discontinued due to AE
- Protocol violation
- Lost to follow-up
- Study terminated
- Non-compliance as defined above in section 6.10

Patients who are withdrawn from the study will not be replaced. The primary reason for patient's withdrawal from the study should be recorded in the source documents and CRF. Subjects will complete an early termination visit.

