7. STATISTICAL AND QUANTITATIVE ANALYSES

7.1 Statistical Methods

More than 50% of patients with CDC T cell crossmatch titers $\geq 1:8$ and/or cPRA $> 80\%$ fail to respond to desensitization (5, 8). In this pilot exploratory, proof of concept, open-label, single-center phase II clinical trial, we hypothesize that our study will have a higher rate of transplantation. [name], PhD, epidemiologist and biostatistician in the division of nephrology, will perform the statistical analyses. *Primary* efficacy (decline in cPRA $> 20\%$) and safety (discontinuation of therapy due to adverse events) endpoint will be analyzed using the exact binomial test. The *secondary* endpoint (time to transplantation) will be assessed using Kaplan-Meier analyses and log rank tests. Baseline characteristics will be compared between participants with and without the primary end point using the 2-sample t test for continuous variables and the Fisher's exact test for categorical variables. Relationships between serum BAFF/APRIL, antibodies, and baseline cPRA will be assessed using the Pearson correlation coefficient. The influence of serum BAFF/APRIL, antibodies, and bone marrow plasma cells on end points of interest will be investigated using Kaplan-Meier curves and Cox proportional-hazards models.

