7.1.6 Efficacy Analysis

Primary outcome will be a decline in cPRA > 20%. Secondary outcome will be kidney transplantation within 12 months of therapy. These outcomes will be assessed using paired t-Test, Kaplan-Meier methods and log rank tests, where appropriate. In addition, we will analyze the change in HLA antibody strength by comparing the MFI values pre and post therapy.

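### Transplantation within 12 months is ascertained only while a patient participates, so patients who stop early have no planned record of transplant status from last contact to month 12

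*Combined protocol and SAP*

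**What the plan says.** Section 3.2 gives the endpoint as "Secondary efficacy endpoint: Successful transplantation in 12 months". Section 7.1.6 words it as "Secondary outcome will be kidney transplantation within 12 months of therapy", without saying when the 12 months start. Section 7.1 treats it as time to event: "endpoint (time to transplantation) will be assessed using Kaplan-Meier analyses and log rank tests".

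Observation follows a different clock. Section 4.3 says "Participants will be followed for the entire length of treatment, plus one month". The paragraph on measurement of effect in Section 6.2 limits the outcome to "whether patients receive a kidney transplant while participating in the study". Section 4.1 sets an early termination visit within one week of discontinuation. Section 6.12 lets the investigator withdraw a patient when study drug is stopped for an adverse event, for a protocol violation, or for the repeated non-compliance defined in Section 6.10. It adds: "Patients who are withdrawn from the study will not be replaced".

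After study follow-up, Section 4.3 passes patients to their dialysis nephrologists. The six-month collection of rejection and survival data is for patients who have been transplanted. Section 7.1.4 allows last observation carried forward where appropriate but has no rule for transplant status. Section 7.1.3 defines only a safety population.

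For completers, Section 4.3 states "Final visit on day 373 + 6, - 3".

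**The concern.** The endpoint needs each patient's transplant status at month 12, whereas the plan collects it up to the end of participation. For a patient who stops in month 3, the remaining nine months are blank, and the plan does not say how to treat them.

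Different readings give different answers. Kaplan-Meier censors the patient at last contact and assumes that the later chance of transplant equals that of the patients still followed. Carrying the last observation forward records a failure. Patients stop for toxicity or poor compliance, and either may be related to the chance of being transplanted. Early stopping may therefore carry information about the outcome.

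The outcome matters to the trial. Section 7.1 hypothesizes a higher transplantation rate, and the objectives box of the Protocol Summary names transplantation within 12 months alongside the cPRA decline. With 10 patients and no replacement, each unknown status moves the possible proportion by 10 percentage points.

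**Working it through.** **The plan's own figures.** Section 7.1.1 gives figures only for the primary cPRA endpoint, and they reproduce. The exact 95% interval for 3/10 is 6.7% to 65.2%. The chance of at least one success at a true rate of 0.2 is 1 − 0.8^10 = 0.893, which is above 80%. They are unaffected by this point. No figure is stated for transplantation.

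**Completers.** The last dose (cycle 12, day 15) is on day 11 × 28 + 15 = 323. The final visit on Day 373 (+6, −3) falls between Days 370 and 379, so the earliest permitted visit is after Day 365 and no endpoint time is lost. However, the schedule also labels this visit as one month after the last dose, and 323 + 30 = 353. That is 12 days short of Day 365, while Day 373 is 50 days after the last dose. The two descriptions disagree.

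**Early stoppers.** Take the last dose to be day 15 of cycle c, that is Day (c − 1) × 28 + 15. Contact ends either 7 days later (early termination visit, assuming discontinuation on the day of the last dose) or 30 days later (one-month follow-up). Days unobserved = 365 − (last dose + 7 or 30).

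| Last cycle | Last dose | Unobserved, +7 | Unobserved, +30 |
|---|---|---|---|
| 3 | Day 71 | 287 | 264 |
| 6 | Day 155 | 203 | 180 |
| 9 | Day 239 | 119 | 96 |

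**Bounds on the proportion.** With x observed transplants and k patients of unknown status, the 12-month proportion lies between x/10 and (x + k)/10. The documents give no dropout rate, so k is an assumption. For x = 2:
- k = 2: 20% to 40%
- k = 3: 20% to 50%
- k = 5: 20% to 70%

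**Kaplan-Meier.** Suppose 3 of 10 are lost before any transplant and 2 of the remaining 7 are transplanted later. The estimate is 1 − (6/7)(5/6) = 2/7 = 28.6%. This lies inside the 20% to 50% range, so the error can go either way.

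**Counting the lost as failures.** Assume a true 12-month rate of 20%, a constant hazard, and loss at month 3. The chance of transplant by month 3 is 1 − 0.8^(3/12) = 5.4%. The expected observed proportion is [(10 − k) × 20% + k × 5.4%]/10, which gives 17.1% (k = 2), 15.6% (k = 3) or 12.7% (k = 5).

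**The case against.** The strongest reply is that this is a secondary endpoint in a 10-patient, single-arm pilot. Kaplan-Meier uses early stoppers up to last contact, so they are not wholly unobserved. Withdrawal after an adverse event is permitted rather than required. A transplant center would probably know of its own transplants anyway.

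The upper bounds are also extreme. Section 1.9 gives 6.9 transplants per 100 active waitlist years at PRA 98% or higher. At that rate, a patient unobserved for 287 days has a chance of 1 − exp(−0.069 × 287/365) = 5.3%. The chance that at least one of three such patients is transplanted unseen is 1 − exp(−3 × 0.069 × 287/365) = 15.0%, and that all three are is 0.053³, about 0.015%. Sampling error is larger: the exact 95% interval for 2/10 is 2.5% to 55.6%.

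Much of this stands, and it limits the weight of the point. It does not close the gap. The 6.9 rate applies only to PRA 98% or higher, while entry is at cPRA 80% or higher, and a patient who responded before stopping could have a higher rate. A patient who stops drug without being withdrawn is still followed for only about a month after the last dose. What the center would notice informally is not a planned ascertainment.

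A reader might also infer that the plan cuts off late responders. The documents do not support this: the endpoint ends at 12 months by definition, and completers are seen after that date. A longer horizon would be a different endpoint, not a repair of follow-up.

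**Conclusion.** The gap holds for patients who stop early and only for them. They have no planned ascertainment of transplant status from last contact to month 12, and no rule says how to analyse them. The unobserved time is 264 to 287 of 365 days for a last dose on Day 71, and less for later stopping. With an assumed 3 of 10 lost and 2 observed transplants, the proportion is bounded only by 20% and 50%. That range rests on an assumed dropout, since the documents give none.

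Counting early stoppers as failures can only leave the proportion unchanged or understate it. One might infer that censoring them inflates the Kaplan-Meier estimate. That would follow only if they were less likely to be transplanted than those still followed, which the documents do not establish.

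The plan should be changed because the remedy is cheap and the outcome is a stated aim. The primary cPRA endpoint and its sample-size figures are untouched.

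**What to change.** - **Sections 3.2 and 7.1.6:** define the endpoint as transplantation within 12 months of first dose. Section 4.2 already treats a patient as enrolled after the first day of ixazomib, so this adds no new reference date.
- **Section 4.3:** collect transplant, death and waitlist status to that date for all 10 enrolled patients from the center's Transplant Database or records, whether or not treatment or study visits have stopped. Add a contact where the database may miss a transplant done elsewhere.
- **Section 7.1:** censor only at withdrawal of consent for record review, and use all enrolled patients as the denominator.
- **Section 6.2:** remove the restriction to the period of participation.
- **Reconcile** the final visit described as one month after last dose (about Day 353) with Day 373. Also reconcile the one-week early termination visit with the one-month monitoring that Section 4.3 promises to all subjects.

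The cost is a record lookup for 10 patients and no visits. Consent must cover record review; the consent pages are not available here, so it may already do so. The documents show that the database is used to find candidates, not that it records transplants at other centers or that patients who stop stay listed. Capture could therefore be incomplete, which is the reason for the extra contact.

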Table 1-1 IXADES Treatment Protocol

| 28-Day Cycle (a 4-week cycle) | | | | | | | | |
|-------------------------------|--------|----------|--------|-----------|--------|------------|--------|------------|
| | Week 1 | | Week 2 | | Week 3 | | Week 4 | |
| | Day 1 | Days 2-7 | Day 8 | Days 9-14 | Day 15 | Days 16-21 | Day 22 | Days 23-28 |
| Ixazomib (NINLARO) 3 mg | ✓ | | ✓ | | ✓ | | | |
| Dexamethasone 20 mg | ✓ | | ✓ | | ✓ | | | |

Figure 1. Study Overview Diagram

Ixazomib for Desensitization (IXADES) in Kidney Transplantation

SCHEDULE OF EVENTS
Table 2-1 (a)-Schedule of events (first six cycles)

| Procedures Performed | Screening (<=/ 30 days) | Cycle 1 (< /= 3 months after screening) | | | Cycle 2 | | Cycle 3 | | | Cycle 4 | | | Cycle 5 | | | Cycle 6 | | |
|------------------------------------|-------------------------|---|---|----|---------|----|---------|----|----|---------|----|----|---------|-----|-----|---------|-----|-----|
| | | 1 | 8 | 15 | 29 | 36 | 43 | 57 | 64 | 71 | 85 | 92 | 99 | 113 | 120 | 127 | 141 | 148 |
| Treatment Days (+6, -3) | | | | | | | | | | | | | | | | | | |
| Ixazomib and Dexamethasone | | X | X | X | X | X | X | X | X | X | X | X | X | X | X | X | X | X |
| Medical History | X | X | | | | | | | | | X | | | X | | | X | |
| Physical Exam | X | X* | | | | | | | | | X | | | | | | | |
| Vital Signs (T, P, R, BP) | X | X | | | X | | | X | | | X | | | X | | | X | |
| AE Assessment | | X | | | X | | | X | | | X | | | X | | | X | |
| Electrocardiogram (ECG) | X | | | | | | | | | | | | | | | | | |
| Echocardiogram | X | | | | | | | | | | | | | | | | | |
| Medication History | X | X | | | X | | | X | | | X | | | X | | | X | |
| Drug Accountability | | | | | X | | | X | | | X | | | X | | | X | |
| Pregnancy Test (where appropriate) | X | | | | | | | | | | | | | | | | | |
| CBC | X | X | | | X | | | X | | | X | | | X | | | X | |
| LFTs | X | X | | X | X | | X | X | X | | X | | | X | | | X | |
| cPRA | | X | | | | | | | | | X | | | | | | | |
| BAFF/APRIL | | X | | | | | | | | | X | | | | | | | |
| DSA Antibodies | | X | | | | | | | | | X | | | | | | | |
| Bone Marrow Aspiration | | X ¹ | | | | | | | | | | | | | | | | |

*Physical examination to be completed at visit 1, if not completed during screening visit.

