1 Bone Marrow Aspiration must be done before drug administration and at one of the following endpoints: one month (+6, -3 days) after the end of the 12 month study, cPRA decline > 20%, time of transplant, or time of subject withdrawal from the study.

Table 2-1 (b)-Schedule of events (last six cycles)

| Procedures Performed | Cycle 7 | | | Cycle 8 | | | Cycle 9 | | | Cycle 10 | | | Cycle 11 | | | Cycle 12 | | | Final visit 1M after last dose | ETV or Unscheduled Visit |
|------------------------------------|---------|-----|-----|---------|-----|-----|---------|-----|-----|----------|-----|-----|----------|-----|-----|----------|-----|----------------|--------------------------------|--------------------------|
| Treatment Days | 169 | 176 | 183 | 197 | 204 | 211 | 225 | 232 | 239 | 253 | 260 | 267 | 281 | 288 | 295 | 309 | 316 | 323 | 373 | |
| Ixazomib and dexamethasone | X | X | X | X | X | X | X | X | X | X | X | X | X | X | X | X | X | X | | |
| Medical History | X | | | | | | | | | X | | | | | | | | | X | |
| Physical Exam | X | | | | | | | | | X | | | | | | | | | X | |
| Vital Signs (T, P, R, BP) | X | | | X | | | X | | | X | | | X | | | X | | X | X | |
| AE Assessment | X | | | X | | | X | | | X | | | X | | | X | | X | X | |
| Electrocardiogram (ECG) | X | | | | | | | | | | | | | | | | | | X | |
| Echocardiogram | X | | | | | | | | | | | | | | | | | | X | |
| Medication History | X | | | X | | | X | | | X | | | X | | | X | | X | X | |
| Drug Accountability | | | | X | | | X | | | X | | | X | | | X | | X | X | |
| Pregnancy Test (where appropriate) | | | | | | | | | | | | | | | | | | | | |
| CBC | X | | | X | | | X | | | X | | | X | | | X | | | X | |
| LFTs | X | | | X | | | X | | | X | | | X | | | X | | | X | |
| cPRA | X | | | | | | | | | X | | | | | | | | | X | |
| BAFF/APRIL | X | | | | | | | | | X | | | | | | | | | X | |
| DSA Antibodies | X | | | | | | | | | X | | | | | | | | | X | |
| Bone Marrow Aspiration | | | | | | | | | | | | | | | | | | X ¹ | X ¹ | |

TABLE OF CONTENTS

| | |
|---|----|
| PROTOCOL SUMMARY..... | 3 |
| STUDY OVERVIEW DIAGRAM (optional)..... | 6 |
| SCHEDULE OF EVENTS..... | 7 |
| LIST OF TABLES AND FIGURES (OPTIONAL)..... | 11 |
| LIST OF ABBREVIATIONS AND GLOSSARY OF TERMS..... | 12 |
| 1. BACKGROUND AND STUDY RATIONALE | 13 |
| 1.1 Scientific Background | 13 |
| 1.1.1 Disease Under Treatment..... | 13 |
| 1.1.2 Ixazomib (MLN9708) | 14 |
| 1.2 Preclinical Experience | 14 |

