Ixazomib is neither a time-dependent inhibitor nor a reversible inhibitor of CYPs 1A2, 2B6, 2C8, 2C9, 2C19, 2D6, or 3A4/5. Ixazomib did not induce CYPs 1A2, 2B6, and 3A4/5 activity or corresponding immunoreactive protein levels. Thus, the potential for ixazomib to produce DDIs via CYP isozyme induction or inhibition is low.

Ixazomib is not a substrate of BCRP, MRP2 and OATPs. Ixazomib is not an inhibitor of Pgp-, BCRP, MRP2, OATP1B1, OATP1B3, OAT1, OAT3, OCT2, MATE1 and MATE2K. Ixazomib- is unlikely to cause or be susceptible to clinical DDIs with substrates or inhibitors of clinically relevant drug transporters.

The geometric mean terminal halflife- ($t_{1/2}$) of ixazomib is 9.5 days based on population PK analysis. For both IV and oral dosing, there is an approximately average 3fold accumulation (based on AUC) following the Day 11 dose for the -twiceweekly- schedule and a 2fold accumulation (based on AUC) following the Day 15 dose for the -onceweekly- schedule.

Mean plasma clearance (CL) of ixazomib is 1.86 L/hr based on the results of a population PK analysis. Taken together with the blood-to-plasma AUC ratio of approximately 10, it can be inferred that ixazomib is a low clearance drug. Using the absolute oral bioavailability (F) estimate of 58% (also from a population PK model), this translates to an apparent oral plasma clearance (CL/F) of 3.21 L/hr. The geometric mean renal clearance for ixazomib is 0.119 L/hr, which is 3.7% of CL/F and 6.4% of CL estimated in a population PK analysis. Therefore, renal clearance does not meaningfully contribute to ixazomib clearance in humans. Approximately 62% of the administered radioactivity in the ADME study (Study C16016) was recovered in the urine and 22% of the total radioactivity was recovered in the feces after oral administration. Only 3.2% of the administered ixazomib dose was recovered in the urine as unchanged ixazomib up to 168 hours after oral dosing, suggesting that most of the total radioactivity in urine was attributable to metabolites.

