2. E-mail may be used throughout the course of the study for the purpose of scheduling study visits and notifying subjects of other study-related information.

Study Procedures

Screening Visit

The screening visit procedures will occur within a 30-day window prior to the Visit 1, Cycle 1 window (3-month window after screening). The following procedures will occur at the screening visit:

- Physical exam
- Medical history (including most recent cPRA results prior to enrollment)
- Vital Signs (Temperature, pulse, respirations, and blood pressure)
- Medication History
- Pregnancy Test (Serum HCG) for females of child-bearing potential
- CBC
- LFTs

Re-screening

Subjects who fail screening may be considered for re-screening if, in the opinion of the principal investigator, their clinical status has changed such that they may now be eligible for study participation per all eligibility criteria. At the discretion of the principal investigator, selected tests, such as lab tests, will not be repeated if previous screening results remain valid per the protocol-defined window for that test.

Visits: Patients will only receive one month's supply of ixazomib and dexamethasone and will return monthly for resupply. At each visit, they will be assessed for AEs by the study team. They will be examined by the principal investigator 5 times (please see tables 2-1 a-b and Figure 1, below): Days 1, 85, 169, 253, and 373 +6, - 3).

- Day 1: Prior to treatment initiation. H&P, Labs, Bone Marrow Aspirate
- Day 85 + 6, - 3: Prior to treatment dose. H&P, Labs
- Day 169 + 6, - 3 Prior to treatment dose. H&P, Labs
- Day 253 + 6, - 3 Prior to treatment dose. H&P, Labs
- Day 373 + 6, - 3 One month after treatment completion, H&P, Labs, Bone Marrow Aspirate
- Study drug will be dispensed at each month's in-person visit, prior the initiation of the next cycle, and after reviewing the AEs and monthly labs.

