- Liver Function tests will be conducted twice a month (+ 6 /- 3 days) for the first 3 months, then monthly thereafter. The complete blood count (CBC) will be checked monthly. cPRA, BAFF/APRIL, DSA and antibodies will be checked every three months (5 times total). Bone marrow aspirates will be collected at the beginning and at one of the following endpoints: one month (+6, - 3 days) after the end of the 12 month study, cPRA decline > 20%, time of transplant, or time of subject withdrawal from the study. ECG and echocardiograms will be done at the baseline, 6 months, and end of the study visits.
- During the first three months of study participation, the bi-weekly Liver Function Tests may be done at the subject's local lab. The local lab will process the sample and send the result to the study team.
- Additional visits may be required if the subject has to hold treatment and needs to return to the clinic for blood draws to confirm eligibility to continue. Please see Table 4-3, Dose Adjustments for Hematologic Toxicities for dose adjustment plan.
- Data on acute rejection, graft and patient survival will be collected for six months after surgery for those subjects who receive a successful kidney transplant.

[figure not shown]
Unscheduled Visits: Subjects may have unscheduled visits due to dose adjustments based on lab results, an acute illness of undetermined cause, for other reasons, or at the discretion of the Investigator. Unscheduled visits may include any of the following procedures;

- Adverse Event Assessment
- Medication History
- Drug Accountability
- Physical Exam
- Vital Signs (Temperature, Pulse, Respirations, Blood Pressure)
- Lab work (CBC, LFTs, cPRA, BAFF/APRIL, DSA Antibodies)
- Bone Marrow Aspiration

Early Termination Visit: All subjects who end study participation prior to the end of the scheduled treatment will undergo an early termination visit within one week from study discontinuation. The early termination visit will consist of the following procedures;

- Adverse Event Assessment
- Medication History
- Drug Accountability
- Physical Exam
- Vital Signs (Temperature, Pulse, Respirations, Blood Pressure)
- Lab work (CBC, LFTs, cPRA, BAFF/APRIL, DSA Antibodies)
- Bone Marrow Aspiration (bone marrow aspiration will be done within 48 hours of transplant)

Figure 1. Study Overview Diagram

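### The final visit is defined as one month after the last dose but fixed at Day 373, 50 days after it, leaving 64 days without a CBC or LFT and 120 days without a cPRA

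*Combined protocol and SAP*

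**What the plan says.** The timing of the final visit is stated in several places.

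- Section 4.3 gives it as "one month following the last dose of study drug to monitor for and address potential adverse events from treatment (Final visit on day 373", +6/-3 days).
- Table 2-1(b) heads the last scheduled column "Final visit 1M after last dose". The day row for cycle 12 and that column reads "309 | 316 | 323 | 373".
- Section 6.2 (Duration of Treatment and Follow-up): "All subjects will be asked to return for a final study visit approximately one month following the last dose of study drug".
- Section 4.1 (Visits) uses a different anchor: "Day 373 + 6, - 3 One month after treatment completion, H&P, Labs, Bone Marrow Aspirate". Sections 7.1.8 and 9.1 also attach Day 373 to completion of treatment, without stating an interval.

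On test frequency, Section 4.1 says: "The complete blood count (CBC) will be checked monthly. cPRA, BAFF/APRIL, DSA and antibodies will be checked every three months (5 times total"). It also sets LFTs at twice a month for three months and monthly after that. In Table 2-1(b), the last CBC and LFT before the final visit are on Day 309 and the last cPRA is on Day 253. Day 323 carries AE assessment, vital signs, medication history and drug accountability, but none of these three blood tests.

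**The concern.** One visit has two definitions, and on the planned schedule no single date satisfies both. For a patient who stops early the two move further apart, because one follows the patient's own last dose and the other is a fixed study day.

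The gap falls where the normal check drops out. In cycles 1 to 11, the CBC at the start of the next cycle comes 14 days after the third dose and also feeds the start-of-cycle criteria in Section 6.3.1. Cycle 12 has no successor, so that check disappears and nothing replaces it. Leucopenia, anemia and thrombocytopenia are named in the primary safety endpoint (Section 3.1), and Section 4.3 gives the detection of adverse events as the purpose of this follow-up. A low count without symptoms cannot be found by asking the patient.

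For efficacy, the Day 253 cPRA is taken before that day's dose (Section 4.1). The only later scheduled value is off drug, so the schedule contains no on-treatment measurement reflecting the final quarter of dosing.

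**Working it through.** **Inputs.** Twelve 28-day cycles with doses on days 1, 8 and 15 (Section 6.2). Test days from Tables 2-1(a) and 2-1(b). Visit window +6/-3 (Section 4.3). Table 2-1(a) labels its day row "Treatment Days (+6, -3"); Table 2-1(b) repeats no window on its own day row.

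**Last dose.** 28 × 11 + 15 = Day 323, which reproduces the table. Cycle 12 ends on 28 × 12 = Day 336.

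**Distance to the final visit.**

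| Reading | Arithmetic | Days |
|---|---|---|
| From last dose, nominal | 373 − 323 | 50 |
| With visit window (Days 370 to 379) | 370 − 323; 379 − 323 | 47 to 56 |
| With dosing window too (last dose Days 320 to 329) | 370 − 329; 379 − 320 | 41 to 59 |
| From end of cycle 12 | 373 − 336 | 37 |

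Thirty days after the last dose is 323 + 30 = Day 353. For Day 373 to be 30 days after the last dose, that dose would have to fall on 373 − 30 = Day 343, which is 20 days later than planned.

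**Test intervals.**

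- CBC and LFTs, cycles 7 to 12: Days 169, 197, 225, 253, 281, 309, 373. The intervals are 28, 28, 28, 28, 28 and 64 days. With a +6/-3 window on both ends, the last is 370 − 315 = 55 to 379 − 306 = 73.
- cPRA: Days 1, 85, 169, 253, 373. The intervals are 84, 84, 84 and 120 days. With windows, the last is 370 − 259 = 111 to 379 − 250 = 129.
- AE assessment: Days 309, 323, 373. The intervals are 14 and 50 days.

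**Doses after the Day 253 sample.** Days 253, 260, 267, 281, 288, 295, 309, 316 and 323: 9 of 36, or 25%.

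**Would moving the visit be enough?** With the final visit on Day 353, the CBC/LFT gap is 353 − 309 = 44 days and the cPRA gap is 353 − 253 = 100 days. Both are shorter, but neither meets the stated interval. A draw 14 days after the last dose (323 + 14 = Day 337) gives 337 − 309 = 28 and 337 − 253 = 84 days, matching the earlier spacing. A draw on Day 323 gives 14 and 70 days, followed by 30 days to a Day 353 visit or 50 days to a Day 373 visit.

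**The case against.** **The anchor.** Section 4.1 counts from completion of treatment, and the footnote to Table 2-1 times the final marrow from the end of the 12-month study. From the end of cycle 12 the excess over a month is about a week, not 20 days. If dosing also ran to the late edge of its window, cycle 12 would end on 336 + 6 = Day 342, and Days 370 to 373 would be 28 to 31 days later. That reconciles the dates only by combining the completion wording with late dosing, and Section 4.3, Section 6.2 and the table header all say last dose. It does not shorten the nominal 64-day and 120-day gaps.

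**Safety.** A reader might infer that the formal safety result is compromised. The documents do not support that. Section 7.1 tests stopping therapy because of an adverse event, and that cannot change after the last dose. Section 8.1.1 counts an abnormal laboratory value as an AE only if it alters treatment, prompts an intervention or is judged clinically significant, and Section 9.1 says the PI will not judge the significance of abstracted results. Further cover comes from the Day 323 AE assessment, discretionary unscheduled visits with laboratory work (Section 4.1) and SAE reporting to 30 days after the last dose (Section 8.2). What remains is patient monitoring: a count low enough to need treatment would qualify as an AE, and without symptoms only a blood test would find it.

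**Efficacy.** A reader might infer that responders will be missed because a late decline in cPRA fades before Day 373. This is conjecture. The half-life "of ixazomib is 9.5 days based on population PK analysis" leaves 0.5^(50/9.5) = 2.6% of the drug at 50 days, but that describes the drug, as does the reversible proteasome binding in Section 1.9. Neither says how fast antibody returns, and Section 1.9 calls it unknown whether ixazomib depletes plasma cells. Any rate of missed response would be invented.

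**Count and purpose.** Five cPRA measurements are promised and five are scheduled; only the last interval departs. A later off-drug value is also a legitimate look at durability. Both points stand, and the second is why keeping Day 373 under a correct label is acceptable.

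**Conclusion.** The concern holds as an internal contradiction with a monitoring gap. The final visit is 50 days after the last scheduled dose, against about 30 stated. The last CBC/LFT interval is 64 days against monthly, and the last cPRA interval is 120 days against three-monthly. These figures assume the nominal schedule; even the shortest windowed gaps, 55 and 111 days, exceed the stated frequencies. The consequence is that cytopenia after the last three doses is not looked for until 50 days off drug, and that the last quarter of dosing has no on-treatment cPRA. Any change in the primary efficacy result is possible but cannot be quantified from the documents. This should be corrected, but it does not undermine the trial.

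**What to change.** **Date.** Choose one definition:

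- Define the final visit as 30 days after the patient's own last dose (nominal Day 353, +6/-3), and use it in Table 2-1(b) and Sections 4.1, 4.3, 7.1.8 and 9.1. Section 6.2 already fits.
- Or keep Day 373 and call it about 50 days after the last dose wherever a month is now stated, including Section 6.2.

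**Blood tests.** In either case add CBC and LFTs, and preferably a locally run cPRA, to the Day 323 contact already in Table 2-1(b), or draw them about 14 days later. Day 323 needs no new visit, but a sample taken before that day's dose reflects only the first two doses of the cycle. The later draw covers all three and restores the 28-day and 84-day spacing, but is an additional attendance.

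**Cost.** One extra blood sample for at most 10 patients, and a protocol amendment with IRB approval (Section 10.1). If cPRA is added, the stated total of five in Sections 4.1 and 9.1 becomes six; leaving the outside antibody panel unchanged keeps the 50 samples in Section 6.14. A draw after Day 323 may also need a line in the visit payments (Section 1.10). Choosing Day 353 shortens the off-drug look at durability by 20 days.
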